8.5 SAFETY REPORTING CRITERIA TO THE PHARMACEUTICAL COLLABORATORS

Reporting will be per the collaborative agreement.

8.6 REPORTING PREGNANCY

All required pregnancy reports/follow-up to OSRO will be submitted to: [contact] and to the CCR PI and study coordinator. Forms and instructions can be found here: <https://ccrod.cancer.gov/confluence/display/CCRCRO/Forms+and+Instructions>

8.6.1 Maternal exposure

If a participant becomes pregnant during the course of the study, the study treatment should be discontinued immediately, and the pregnancy reported to the Sponsor no later than 24 hours of when the Investigator becomes aware of it. The Investigator should notify the Sponsor no later than 24 hours of when the outcome of the Pregnancy becomes known.

Pregnancy itself is not regarded as an SAE. However, congenital abnormalities or birth defects and spontaneous miscarriages that meet serious criteria (Section [8.1.2](#)) should be reported as SAEs.

The outcome of all pregnancies should be followed up and documented.

8.6.2 Paternal exposure

Male participants should refrain from fathering a child or donating sperm during the study and for 125 days after the last dose of bintrafusp alfa.

Pregnancy of the participant's partner is not considered to be an AE. The outcome of all pregnancies occurring from the date of the first dose until 125 days after the last dose should, if possible, be followed up and documented. Pregnant partners may be offered the opportunity to participate in an institutional pregnancy registry protocol (e.g., the NIH IRP pregnancy registry study) to provide data about the outcome of the pregnancy for safety reporting purposes.

8.7 REGULATORY REPORTING FOR STUDIES CONDUCTED UNDER CCR-SPONSORED IND

Following notification from the investigator, CCR, the IND sponsor, will report any suspected adverse reaction that is both serious and unexpected. CCR will report an AE as a suspected adverse

reaction only if there is evidence to suggest a causal relationship between the study product and the adverse event. CCR will notify FDA and all participating investigators (i.e., all investigators to whom the sponsor is providing drug under its INDs or under any investigator's IND) in an IND safety report of potential serious risks from clinical trials or any other source, as soon as possible, in accordance to 21 CFR Part 312.32.

All serious events will be reported to the FDA at least annually in a summary format.

8.8 SPONSOR PROTOCOL DEVIATION REPORTING

A Protocol Deviation is defined as any non-compliance with the clinical trial Protocol, Manual of Operational Procedures (MOP) and other Sponsor approved study related documents, GCP, or protocol-specific procedural requirements on the part of the participant, the Investigator, or the study site staff inclusive of site personnel performing procedures or providing services in support of the clinical trial.

It is the responsibility of the study Staff to document any protocol deviation identified by the Staff or the site Monitor in the CCR Protocol Deviation Tracking System (PDTs) online application. The entries into the PDTs online application should be timely, complete, and maintained per CCR PDTs user requirements.

In addition, any deviation to the protocol should be documented in the participant's source records and reported to the reviewing IRB per their guidelines. OSRO required protocol deviation reporting is consistent with E6(R2) GCP: Integrated Addendum to ICH E6(R1): 4.5 Compliance with Protocol; 5.18.3 (a), and 5.20 Noncompliance; and ICH E3 16.2.2 Protocol deviations.

9 CLINICAL MONITORING

Clinical site monitoring is conducted to ensure:

- that the rights of the participants are protected;
- that the study is implemented per the approved protocol, Good Clinical Practice and standard operating procedures; and,
- that the quality and integrity of study data and data collection methods are maintained.

Monitoring for this study will be performed by NCI CCR Office of Sponsor and Regulatory Oversight (OSRO) and Regulatory Oversight Support (SROS) Services contractor. Clinical site monitoring activities will be based on OSRO standards, FDA Guidance E6(R2) Good Clinical Practice: Integrated Addendum to ICH E6(R1) March 2018, and applicable regulatory requirements.

Details of clinical site monitoring will be documented in a Clinical Monitoring Plan (CMP) developed by OSRO. CMPs will be protocol-specific, risk-based and tailored to address human subject protections and integrity of the study data. OSRO will determine the intensity and frequency of monitoring based on several factors, including study type, phase, risk, complexity, expected enrollment rate, and any unique attributes of the study and the site. The Sponsor will conduct a periodic review of the CMP to confirm the plan's continued appropriateness. A change to the protocol, significant or pervasive non-compliance with GCP, or the protocol may trigger CMP updates.

OSRO SROS Monitoring visits and related activities will be conducted throughout the life cycle of each protocol. The first activity is before the study starts to conduct a Site Assessment Visit

(SAV) (as warranted), followed by a Site Initiation Visit (SIV), Interim Monitoring Visit(s) (IMVs), and a study Close-Out Visit (COV).

Some monitoring activities may be performed remotely, while others will occur at the study site. Monitoring visit reports will describe visit activities, observations, and associated action items or follow-up required for resolution of any issues, discrepancies, or deviations. Monitoring reports will be distributed to the study PI, NCI CCR QA, CCR Protocol Support Office, coordinating center (if applicable) and the Sponsor regulatory file.

The site Monitor will inform the study team of any deviations observed during monitoring visits. If unresolved, the Monitor will request that the site Staff enter the deviations in the CCR Protocol Deviation Tracking System (PDTs) for deviation reporting to the Sponsor and as applicable per institutional and IRB guidance.

10 STATISTICAL CONSIDERATIONS

10.1 STATISTICAL HYPOTHESIS

10.1.1 Primary Efficacy Endpoint

To assess Overall Response Rate (ORR) according to RECIST 1.1.

10.1.2 Secondary Efficacy Endpoints

To assess:

- Safety and tolerability of bintrafusp alfa in participants with recurrent or metastatic ONB
- Progression Free Survival
- Duration of response
- Overall Survival

10.2 SAMPLE SIZE DETERMINATION

There is no published literature on the anticipated efficacy of any specific treatment for participants with ONB. In these rare participants, the objective will be to determine if a modest response rate is possible while keeping the study size small. Thus, in immune checkpoint-naïve participants, this trial will be conducted using a Simon optimal two-stage phase II trial design (Simon R, Controlled Clinical Trials 10:1-10, 1989) to rule out an unacceptably low response rate (CR+PR) of 5% ($p_0=0.05$) in favor of an improved response rate of 20% ($p_1=0.20$). With $\alpha=0.10$ (one sided alpha; equals two-sided alpha = 0.20; probability of accepting a poor treatment=0.10) and $\beta=0.20$ (probability of rejecting a good treatment=0.20), the first stage will enroll 12 evaluable participants, and if 0 of the 12 has a response, then no further participants will be accrued. If 1 or more of the first 12 participants has a response, then accrual would continue until a total of 21 evaluable participants have been treated. As it may take up to several months to determine if a participant has experienced a response, a temporary pause in the accrual may be necessary to ensure that enrollment to the second stage is warranted. If there are 1-2 participants with a response out of 21 participants, this would likely be an uninterestingly low response rate. If there were 3 or more of 21 (14.3%) who experienced a response, this would be sufficiently interesting to warrant further study in later trials. Even if there are fewer than 3 responses, this will provide information on degree of efficacy of a single agent in a rare disease where there is currently no published

information. Under the null hypothesis (5% response rate), the probability of early termination is 54.0%.

It is expected that approximately 6-8 participants per year may enroll on this trial. Thus, in order to enroll up to 21 evaluable CN participants, it is expected that accrual will be completed within 3 to 4 years. We will also enroll up to 8 immune checkpoint-resistant (CR) participants; this cohort will be evaluated separately for OR. Accrual for CR participants will occur in two stages: initially 5 CR participants will be enrolled; if responses are observed in one or more participants, the second stage will enroll another 3 participants. Accrual for CR participants will end when the needed number of CN participants have been accrued. To allow for a small number of inevaluable participants, the accrual ceiling will be set at 32 participants (21 in the main CN cohort, 8 in the exploratory CR cohort, and 3 additional participants for inevaluable).

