10.4 STATISTICAL ANALYSES

10.4.1 Analysis of the Primary Endpoints

The fraction of evaluable participants who experience a response will be reported along with a 95% two-sided confidence interval.

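### Does it matter that Section 10.2 calls the 12/21 design Simon optimal when it is the minimax design?

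*Combined protocol and SAP*

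**What the plan says.** Section 10.2 names the method: "this trial will be conducted using a Simon optimal two-stage phase II trial design". The purpose is to "determine if a modest response rate is possible while keeping the study size small". The design sets an "unacceptably low response rate (CR+PR) of 5" per cent against an "improved response rate of 20" per cent, with alpha 0.10, described as "one sided alpha; equals two-sided alpha = 0.20; probability of accepting a poor treatment=0.10", and beta 0.20.

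The rules follow in full. Twelve evaluable checkpoint-naïve participants enter the first stage, and accrual stops if none responds. Otherwise accrual goes on to 21. One or two responses of 21 count as uninteresting. The success rule begins "If there were 3 or more of 21 (14.3%) who experienced a response". Early termination under the 5% rate is given as 54.0%. Later in the same section "the accrual ceiling will be set at 32 participants (21 in the main CN cohort, 8 in the exploratory CR cohort", with 3 more places for inevaluable participants.

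On the analysis, Section 10.4.1 says: "The fraction of evaluable participants who experience a response will be reported along with a 95% two-sided confidence interval". It names no interval method and does not repeat the 3-of-21 rule.

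**The concern.** Optimal and minimax are defined criteria for a Simon two-stage design. Among all designs that meet the two error limits, the optimal one has the smallest expected sample size under the null rate, and the minimax one has the smallest maximum sample size. They usually differ, so a reader who sees the first label can check it and find that the stated numbers do not fit.

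Two things might be at stake. If the label is right and the numbers are wrong, the trial has the wrong stage sizes, and the 32-participant ceiling rests on the wrong total. If the numbers come from a faulty search, the error rates may not hold.

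A second worry attaches to Section 10.4.1. A 95% two-sided interval works at 2.5% per tail, while the decision rule works at 10% in one tail. A result of exactly 3 of 21 could pass the rule while the interval still contains 5%.

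**Working it through.** **Inputs (Section 10.2).** p0 = 0.05, p1 = 0.20, alpha ≤ 0.10 one-sided, power ≥ 0.80; n1 = 12, stop at 0 responses; n = 21, success at 3 or more.

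**The plan's own figure.** Early termination under p0 = 0.95^12 = 0.5404, which is the stated 54.0%.

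**Error rates of the design as written.** Success needs 1 response in stage 1 and at least 2 of 9 in stage 2, or 2 and at least 1 of 9, or 3 or more in stage 1.

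- Under 5%: 0.3413 × 0.0712 + 0.0988 × 0.3698 + 0.0196 = 0.0243 + 0.0365 + 0.0196 = 0.0804.
- Under 20%: 0.2062 × 0.5638 + 0.2835 × 0.8658 + 0.4417 = 0.803.
- Expected size under p0: 12 + (1 − 0.5404) × 9 = 16.14.

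Both limits are met. The attained alpha lies below 0.10 because response counts are discrete.

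**Which design is it?** An exact-binomial search over all two-stage designs with n up to 45, keeping those with alpha ≤ 0.10 and power ≥ 0.80, gives the lowest expected size for each maximum size:

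| Maximum n | Design | Alpha | Power | Early stop under p0 | Expected n under p0 |
|---|---|---|---|---|---|
| 21 | 0/12, 2/21 | 0.0804 | 0.8033 | 54.0% | 16.14 |
| 22 | 0/11, 2/22 | 0.0862 | 0.8126 | 56.9% | 15.74 |
| 23 | 0/10, 2/23 | 0.0905 | 0.8133 | 59.9% | 15.22 |
| 24 | 0/9, 2/24 | 0.0931 | 0.8047 | 63.0% | 14.55 |

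No design with n below 21 qualifies, and from 25 upwards the expected size is above 16. So 0/12, 2/21 is minimax and 0/9, 2/24 is optimal. Rounding does not explain the difference: 16.14 − 14.55 = 1.59 participants.

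**The interval.** Section 10.4.1 names no method, so Clopper-Pearson is assumed.

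| Result | Exact 95% interval | Exact 80% interval | 3-of-21 rule |
|---|---|---|---|
| 2/21 | 1.2% to 30.4% | 2.6% to 23.4% | not met |
| 3/21 | 3.0% to 36.3% | 5.4% to 29.1% | met |
| 4/21 | 5.4% to 41.9% | 8.6% to 34.5% | met |

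The 95% interval and the rule point different ways only at exactly 3/21, which has probability 18.0% if the true rate is 20% and 6.2% if it is 5%. Allowing for the two-stage stopping moves the 95% limits at 3/21 only to 3.1% and 36.7%. It matters more at low counts: the 95% upper limit goes from 23.8% to 27.8% at 1/21 and from 30.4% to 31.6% at 2/21. At those counts the rule is not met and 5% lies inside the interval either way.

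**The case for a change.** The best case for a correction is that the label is a checkable technical claim and is false. A reader who regenerates an optimal design from the stated inputs gets 24 participants, which would make the ceiling 24 + 8 + 3 = 35 instead of 21 + 8 + 3 = 32. The wrong word could also pass into the final report. Putting it right costs one word. On the interval, one sentence in Section 10.4.1 and an added 80% interval would align the reported precision with the 10% rule, at the price of one more number to report.

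The first part stands as a matter of terminology. The consequence does not. To reach 24, a reader must set aside the explicit stage sizes: 12 and then 9 more for 21 in the Précis, up to 21 in Section 3.1, 12 and 21 in Section 10.2, and the 12-participant interim look in Section 10.4.5. The stated 54.0% belongs to a first stage of 12; a first stage of 9 would give 63.0%. The numbers therefore show which design was meant.

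The interval point is a preference. Section 10.2 already gives the decision rule and says openly that its one-sided 10% corresponds to a two-sided 20%. Section 10.4.1 only reports an interval and attaches no success criterion to it, so there is no second rule to rank against the first. A conventional 95% interval beside a screening rule at 10% is ordinary practice in a small phase 2 trial.

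**Conclusion.** This is a clerical slip in one word of Section 10.2. The design is Simon minimax, not Simon optimal, and it is correctly computed: attained alpha 0.080 against a limit of 0.10, power 0.803 against 0.80, early termination 54.0% as stated. Choosing minimax costs 1.59 expected participants under the null and saves 3 at the maximum (21 against 24), a fair trade in a rare disease where the aim is to keep the study small.

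Correcting the word would alter no participant number, cut-off, error rate, result or conclusion, and the written rules leave an analyst nothing to guess. The interval in Section 10.4.1 needs no change either, since the 3-of-21 rule alone decides and the interval describes precision.

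The design result rests only on the inputs stated in Section 10.2 and exact binomial probabilities. The interval figures assume Clopper-Pearson. A Wilson 95% lower limit at 3/21 is 4.98%, which also just includes 5%.

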10.3 POPULATIONS FOR ANALYSES

Intention to treat: any subjects who enroll onto the trial and provide consent and who receive at least one dose of bintralusp alfa will be included in the efficacy and safety evaluations. Only the immune checkpoint-naïve participants will be included in the primary endpoint analysis. The CN and CR populations will be reported separately for the secondary and exploratory endpoints.

10.3.1 Evaluable for Toxicity

All participants will be evaluable for toxicity from the time of their first treatment with bintralusp alfa.

10.3.2 Evaluable for Objective Response

Only those participants who have measurable disease present at baseline, have received at least one cycle of therapy, and have had their disease re-evaluated will be considered evaluable for response. These participants will have their response classified according to the definitions stated in Section 6.3 (Note: Participants who exhibit objective disease progression prior to the end of cycle 1 will also be considered evaluable.)

10.3.3 Evaluable Non-Target Disease Response:

Participants who have lesions present at baseline that are evaluable but do not meet the definitions of measurable disease, have received at least one cycle of therapy, and have had their disease re-evaluated will be considered evaluable for non-target disease. The response assessment is based on the presence, absence, or unequivocal progression of the lesions.

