10.4.2 Analysis of the Secondary Endpoint(s)

PFS will be determined using the Kaplan-Meier method and will be reported along with 95% confidence intervals. PFS will be defined as the time from the date of first treatment to the date of disease progression or death (any cause) whichever occurs first. Subjects who do not have disease progression or have not died at the end of follow up will be censored at the last known date the subject was progression free.

OS will be evaluated using Kaplan-Meier methods. OS will be defined as the time from the date of first treatment to the date of death (any cause). Subjects who are alive at the end of follow up will be censored at the last known date alive.

Duration of Response: The duration of overall response is measured from the time measurement criteria are met for CR or PR (whichever is first recorded) until the first date that PD or death is objectively documented and is evaluated using the Kaplan-Meier method. Analysis of safety and tolerability is as described in the Section **10.4.3**.

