17.3 APPENDIX C: BEST OVERALL RESPONSE PER RECIST 1.1

RECIST version 1.1 will be used in this study for assessment of tumor response.(1)

For Participants with Measurable Disease (i.e., Target Disease)

Target Lesions	Non-Target Lesions	New Lesions	Overall Response	Best Overall Response when Confirmation is Required*
CR	CR	No	CR	≥ 4 wks. Confirmation**
CR	Non-CR/Non-PD	No	PR	≥ 4 wks. Confirmation**
CR	Not evaluated	No	PR	
PR	Non-CR/Non-PD/not evaluated	No	PR	
SD	Non-CR/Non-PD/not evaluated	No	SD	Documented at least once ≥ 4 wks. from baseline**
PD	Any	Yes or No	PD	no prior SD, PR or CR
Any	PD***	Yes or No	PD	
Any	Any	Yes	PD	

* See RECIST 1.1 manuscript for further details on what is evidence of a new lesion.
 
** Only for non-randomized trials with response as primary endpoint.
 
*** In exceptional circumstances, unequivocal progression in non-target lesions may be accepted as disease progression.
 
Note: Participants with a global deterioration of health status requiring discontinuation of treatment without objective evidence of disease progression at that time should be reported as “symptomatic deterioration.” Every effort should be made to document the objective progression even after discontinuation of treatment.
				

For Participants with Non-Measurable Disease (i.e., Non-Target Disease)

Non-Target Lesions	New Lesions	Overall Response
CR	No	CR
Non-CR/non-PD	No	Non-CR/non-PD*
Not all evaluated	No	not evaluated
Unequivocal PD	Yes or No	PD
Any	Yes	PD

* 'Non-CR/non-PD' is preferred over 'stable disease' for non-target disease since SD is increasingly used as an endpoint for assessment of efficacy in some trials so to assign this category when no lesions can be measured is not advised

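### Sections 10.3 and 10.4.1 give different denominators for the primary ORR, and the evaluable-only one drops dosed participants who are never re-evaluated

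*Combined protocol and SAP*

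**What the plan says.** All references are to the combined protocol and SAP.

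- **Section 10.3**, under an intention-to-treat label, says that consented, enrolled participants "who receive at least one dose of bintralusp alfa will be included in the efficacy and safety evaluations". The only narrowing it makes for the primary endpoint is to the CN cohort.
- **Section 10.3.2** counts as response-evaluable those with measurable baseline disease who "have received at least one cycle of therapy, and have had their disease re-evaluated will be considered evaluable for response". Its note adds: "Participants who exhibit objective disease progression prior to the end of cycle 1 will also be considered evaluable". The documents do not define a cycle for the every-2-week schedule.
- **Section 10.4.1**: "The fraction of evaluable participants who experience a response will be reported along with a 95% two-sided confidence interval".
- **Section 10.2** counts the design in evaluable participants: stop at 0 responses in 12, otherwise "accrual would continue until a total of 21 evaluable participants have been treated", with 3 or more responses as the success threshold. It also says: "To allow for a small number of inevaluable participants, the accrual ceiling will be set at 32 participants". That is 21 CN, 8 checkpoint-resistant and 3 spare places, not divided between cohorts. Section 10.4.5 uses 12 evaluable CN participants at the interim.
- **Section 10.4.2** measures PFS and OS from first treatment, with no evaluability condition.
- **Appendix C** gives a reporting label to "global deterioration of health status requiring discontinuation of treatment without objective evidence of disease progression", but does not say how it counts in the ORR.

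**The concern.** The two rules give different denominators for the same primary estimate. The more specific rule in 10.4.1 presumably governs, but 10.3 does not say so, and no all-dosed ORR is planned.

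Under 10.4.1, a dosed CN participant who dies, withdraws, stops for toxicity or deteriorates before any disease re-evaluation, and without documented objective progression, leaves the denominator. A spare place can then be used to replace that person. The same early death is a PFS event. Leaving the denominator in this way is probably related to poor outcome, and scheduled restaging comes only every 8 weeks (Section 6.3).

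At stake is the primary estimate and its interval in a cohort of 21, in a disease for which Section 10.2 reports no published efficacy data.

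**Working it through.** **1. Reproduce the plan's design.** Inputs from Section 10.2: p0 = 0.05, p1 = 0.20, one-sided alpha 0.10, beta 0.20, stop at 0/12, success at 3 or more of 21.

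- Early termination under p0: 0.95^12 = 0.540, matching the stated 54.0%.
- P(success) = sum over x = 1 to 12 of Bin(x; 12, p) × P(Y ≥ 3 − x), with Y ~ Bin(9, p). This gives 0.080 at p = 0.05 and 0.803 at p = 0.20.

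Both are within the stated limits, for evaluable participants.

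**2. Direction for participants never re-evaluated.** Section 6.3 asks for repeat imaging to confirm a complete or partial response, so someone with no re-evaluation cannot be a recorded responder. Removing k such people from n leaves r responders: r/(n − k) ≥ r/n, with equality when r = 0.

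**3. Direction for the one-cycle condition.** This condition is separate. Study Calendar note 10 continues tumour assessment after treatment ends in participants without progression. Someone who stops before completing a cycle, whatever its length, may therefore be assessed later and still be excluded. If that person is a non-responder, exclusion raises the ORR. If a responder, it lowers it: dropping one of 4 responders among 22 dosed turns 4/22 = 18.2% into 3/21 = 14.3%.

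**4. Size.** Take 21 evaluable CN participants plus 0 to 3 unevaluated ones counted as non-responders. The maximum of 24 (21 + 3) assumes that all shared spare places go to CN. Intervals are Clopper-Pearson 95%.

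| Denominator | 3 responses | 4 responses |
|---|---|---|
| 21 (evaluable only) | 14.3% (3.0 to 36.3) | 19.0% (5.4 to 41.9) |
| 22 | 13.6% (2.9 to 34.9) | 18.2% (5.2 to 40.3) |
| 23 | 13.0% (2.8 to 33.6) | 17.4% (4.95 to 38.8) |
| 24 | 12.5% (2.7 to 32.4) | 16.7% (4.7 to 37.4) |

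With 3 responses the shift is 14.29 − 13.64 = 0.65 to 14.29 − 12.50 = 1.79 percentage points, and every interval includes 5%. With 4 responses the lower limit passes below 5% only when at least 2 unevaluated participants are counted. With 5 responses even 5/24 = 20.8% has a lower limit of 7.1%.

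**5. Error rates if the 5% null referred to all dosed participants.** Each dosed participant is unevaluated with probability f (assumed) or responds with probability 0.05. Accrual stops at 0/12 evaluable, at 21 evaluable or at 24 dosed. Type I error is 0.090 at f = 5%, 0.098 at 9.4% and 0.099 at 10%, and passes 0.10 only above about 10.5%. The 9.4% is 3/32, an accrual allowance across both cohorts and not a forecast for CN. With the null on evaluable participants, as Section 10.2 is written, the same cap gives 0.080, 0.078 and 0.078.

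**The case against.** The strongest reply is that the plan is coherent. Sections 10.2, 10.4.1 and 10.4.5 all count evaluable participants, and 10.2 allows for the rest. Section 10.3 can be satisfied through PFS and OS, which are efficacy evaluations with no evaluability condition. The excluded group is also small. Extra scans are allowed, assessment continues after treatment, and Appendix C asks for progression to be documented after deterioration. The criterion is re-evaluation, and Section 6.3 lists physical examination among tumour assessments, so a missing scan alone does not exclude anyone. Finally, moving the estimate to all dosed participants separates it from the decision rule: a trial could meet 3/21 while reporting 3/24 = 12.5%.

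Much of this stands. The counting rule is deliberate, and the group is small. But 10.3 goes straight on to the primary endpoint and narrows it only to CN, so its text does not confine itself to PFS and OS. The safeguards shrink the excluded group without removing it, and the plan itself expects some inevaluable participants. The split between estimate and decision rule is a real cost, met by stating it. Keeping the evaluable ORR as primary with an all-dosed sensitivity analysis would show the same two figures. It would, however, leave the main result on a set defined by what happens after dosing, and at odds with 10.3.

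A reader might infer three stronger points that the documents do not support:

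- **That the Simon error rates are broken.** They are stated for evaluable participants and hold there. Step 5 exceeds 0.10 only under a null the plan does not state and above about 10.5% unevaluated.
- **That the denominator decides the result at 4 responses.** The crossing of 5% needs exactly 4 responses and at least 2 unevaluated CN participants. No go/no-go rule uses the interval, and at the plan's own threshold, 3/21, it already includes 5%.
- **That every exclusion under 10.3.2 inflates the ORR.** That holds for participants never re-evaluated, not for the one-cycle condition.

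**Conclusion.** The point holds. The plan gives two denominators for its primary ORR and does not say which governs. The evaluable-only one removes dosed CN participants who cannot be recorded responders, so to that extent the ORR is raised or unchanged. The undefined cycle condition adds an ambiguity of unknown direction.

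The size is modest: about 0.6 to 1.8 percentage points at 3 responses, inside an interval more than 30 points wide. This assumes 21 evaluable CN participants and one to three unevaluated ones. No accrual or success decision changes. It is worth correcting because it affects the primary estimate, can be settled before results are known, and costs little.

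**What to change.** In Sections 10.3, 10.3.2 and 10.4.1:

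- Report the primary ORR and its 95% interval among all CN participants who received at least one dose, counting anyone without a post-baseline assessment as a non-responder.
- Report the evaluable-only ORR alongside as a labelled sensitivity analysis.
- State which set governs the ORR.
- Define cycle for this analysis, or remove it from the evaluability definition.

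Keep the 0/12 and at-least-3/21 evaluable counts, and the allowance for inevaluable participants, as the accrual decision rule. Add a sentence that its error rates refer to evaluable participants, and that the reported all-dosed ORR may therefore fall slightly below the 14.3% that corresponds to 3/21.

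The cost is wording and a possibly slightly lower reported ORR. Sample size, accrual and thresholds do not change.
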